Active Intervention. Six cooking classes will be held every week for six consecutive weeks. The cooking lessons will be patterned after [name] cooking pedagogy and will be tailored for individuals cooking for themselves for the first time. Classes will begin with a brief lecture on the day's topic, followed by a laboratory session. Participants work in teams of two in the NFS foods lab to actively practice skills and cook a meal. Subjects will receive recipes and information sheets that cover pantry supplies, grocery lists, knife skills and cooking equipment. Classes will be taught by a chef trained in the pedagogy by [name] and participants will have the opportunity to sample the food they prepared at the end of class.

Kitchen Intensive. As part of the orientation process, participants will attend a 2-hour kitchen intensive demonstration. This demonstration will introduce participants to the kitchen lab space and cover basic kitchen skills including food safety, sanitation, equipment overview, and the basic principles of food agency.

Control Condition. Those in the Control Condition will receive no cooking support over the fall semester. They will serve as a benchmark for how college students normally cook without focused instruction. They will be asked to fill out all measures at baseline and throughout the intervention and will be incentivized to do so.

Phase 2 and Phase 3: Follow up Support

The active and control groups receiving follow up support (groups A and C) will receive six weeks of meal kits immediately following the start of the spring semester. Participants in these groups will receive a single delivery each week that will contain three dinner meal kits designed to feed 2 people. The kits will contain all of the ingredients and instructions needed to prepare the recipes, though participants must cook the meals themselves. After six weeks of receiving meal kits, groups will receive five healthy recipes via email per week. Recipes will be designed by the research team, which includes three registered dietitians and a trained chef. Participants will need to shop, budget, and plan on their own.

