Following signed consent participants will be asked to complete a few baseline tasks to be fully eligible for participation in the study. These tasks include three days of food tracking using ASA-24, baseline surveys, submission of cooking frequency and food photos, and finally a one-on-one interview with study staff to discuss their participation. These baseline tasks are intended to ensure participant compliance and retention during the 18-week intervention.

Eligible participants will be assigned to one of four scheduled class periods based on their stated availability or recruited for the control condition. Once all classes are full, a random assignment table will be used to determine the group assignment for each class period. Participants will then be informed of their group assignment (active with follow up or active no follow up). Participants who are in the control condition will be randomly assigned to either a group that receives follow-ups or a group that does not. Groups will not be stratified by any criteria, and instead will be determined based upon participant availability.

Surveys will be administered through the study REDCap website at baseline and study end. Participants will receive links to the questionnaires and reminders to complete questionnaires via email. These measures are outlined in greater detail below. In addition to questionnaires, weekly data collection (Photo Elicitation and Cooking Frequency) will be administered through REDCap. Participants will receive a weekly email with links to a REDCap data collection tool. Participants will receive reminders to complete weekly data submissions, and will be given information regarding a helpline for using the study website and data entry.

Table 1 outlines when each measure will occur during the study.

Measures	Baseline	Weekly	Phase 1	Phase 2	Phase 3
ASA24					
HEI (calculated)					
CAFPAS					
Cooking Perceptions and Behaviors					
PSS					
Intuitive Eating Scale					
Interoceptive Awareness					
Cooking Frequency					
Photo Elicitation					
Class Evaluation					
Meal Kit Evaluation				X	
COVID-19 Questionnaire					X

Quantitative Measures

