A repeated measures ANOVA analysis will be used to compare changes in intuitive eating, diet quality and food agency over time both within the groups and between the groups. A generalized linear mixed model design will be used to compare the frequency of cooking at home each week over time and between the groups.

Aim 2: To evaluate if providing students with six weeks of a meal delivery service and then six weeks of recipes after completion of cooking classes maintains gains in diet quality, cooking frequency, intuitive eating, and food agency.

Hypothesis 2a: Meal delivery service will better maintain cooking frequency, intuitive eating skills, food agency and diet quality versus recipe provision only. Both meal delivery service and recipe provision will result in more frequent cooking, higher food agency, and higher diet quality the provision of no cooking support.

Hypothesis 2b: During both meal delivery service provision and recipe provision, those in the Cooking Class Condition will maintain higher levels of food agency, cooking frequency, and diet quality than those in the Control Condition.

Repeated measures ANOVA analyses will be used to compare between subjects effects from the meal delivery and recipe only interventions, as well as to compare the material support interventions against the control group. Repeated measures ANOVA will also be used to compare within subjects effects from end of fall semester to the end of each six-week material support intervention.

Aim 3: To positively influence participants' stress levels.

Hypothesis 3: Participants receiving cooking support will have lower scores on a measure of perceived stress than participants who do not receive cooking support. This will be true at all measurement time points.

A repeated measures ANOVA will be used to determine differences both between groups and over time in scores of perceived stress.

Aim 4: To explore the reasons why students cook or do not cook.

Hypothesis 4: There will be common themes defining why student choose to cook or not cook at home.

This is an exploratory aim, and qualitative analysis will be used to deduce popular themes.

Sample Size

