This is a pilot study with no previous data available to calculate expected statistical power. The sample size chosen was practical as our foods lab can only accommodate 16 people at a time. One group of each intervention arm (four) would give us data on approximately 64 subjects. This preliminary data will be used to determine the sample size power needed for a larger study with sufficient statistical power.

Inclusion/Exclusion Criteria: Eligibility and ineligibility criteria should be specific. Describe how eligibility will be determined and by whom. Changes to the eligibility criteria at a later phase of the research have the potential to invalidate the research.

Interested individuals will be directed to a study application that provides details about the study program and asks a series of screening questions. These questions are intended to determine basic eligibility for the study. Ineligible applicants will be notified of their ineligibility and directed to other campus resources related to cooking and meal planning. Eligible applicants will be directed to sign up for an in-person information session.

Inclusion criteria:

- Student at the University of Vermont
- Age 18-25
- Cooks dinner at home no more than 3x/week
- Access to a kitchen at home
- Lives independently off campus (may have roommates but may not live with guardians)
- Availability during scheduled cooking classes/demonstrations

Individuals will be excluded from the study if they do not complete baseline data collection measures prior to the first class meeting. Baseline data measures include four questionnaires (PSS, CAFPAS, Cooking Behavior, and intuitive eating scale), three days of ASA-24 logs, one photo elicitation survey, and one cooking frequency survey.

Inclusion of Minorities and Women: Describe efforts to include minorities and women. If either minorities or women are excluded, include a justification for the exclusion.

Women and minorities will be included. During recruitment, we will work with UVM Office of Student and Community Relations to ensure that our recruitment materials and procedures capture eligible students of all demographics.

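### Aim 2 and Aim 3, support versus no support: adjusting for the two pre-support values already collected is usually more precise than the planned repeated measures ANOVA without covariates, but the gain can be close to nil

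*Combined protocol and SAP*

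**What the plan says.** Statistical Considerations, Aim 2, plans a between-subjects repeated measures ANOVA of the meal kit and recipe phases, "as well as to compare the material support interventions against the control group". Read with Hypothesis 2a, that control group is most naturally the groups without support (B and D), so the contrast is A+C versus B+D. The section adds: "Repeated measures ANOVA will also be used to compare within subjects effects from end of fall semester to the end of each six-week" support period. For stress under Aim 3: "A repeated measures ANOVA will be used to determine differences both between groups and over time in scores of perceived stress". No covariate and no rule for missing data is given. Weekly cooking frequency has a generalized linear mixed model, but that sentence stands under Aim 1 only.

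The opening summary, Study Design and the survey-administration text after Follow-up Data Collection place assessments at baseline and after each phase, for all groups. Quantitative Measures has the stress scale every six weeks. One sentence in Procedures instead places the surveys at baseline and study end only.

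Support is allocated at random in two ways (Procedures). For class students, "a random assignment table will be used to determine the group assignment for each class period". For controls: "Participants who are in the control condition will be randomly assigned to either a group that receives follow-ups or a group that does not".

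**The concern.** Support is the factor whose random allocation the documents describe most consistently. The sample is fixed by kitchen capacity, so the choice of analysis is one of the few remaining means of gaining precision. Baseline and end-of-Phase-1 values both precede support and should predict the Phase 2 and Phase 3 outcomes. An ANOVA without covariates uses them only as levels of the repeated outcome, or not at all. A change score fixes the coefficient of the earlier value at 1, and a post-only comparison fixes it at 0; covariate adjustment estimates it. What is at stake is the width of the intervals from a pilot that is meant to inform a larger study.

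**Working it through.** **The plan's own figure.** 4 groups × 16 = 64 (Sample Size; Number of Subjects). This is capacity arithmetic, and it reproduces. There is no stated power to check.

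**Inputs.** From the documents: 32 with support and 32 without; within controls, 16 (C) versus 16 (D); measurements at baseline, end of Phase 1, end of Phase 2 and end of Phase 3. Assumed: unit variance, correlation r, complete data, no clustering. The outcome is the end-of-Phase-2 value.

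**Variance per person.**

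| Analysis | Compound symmetry | Equally spaced AR(1) |
|---|---|---|
| Post-only | 1 | 1 |
| Change from end of Phase 1 | 2(1−r) | 2(1−r) |
| Phase 2 minus mean of both pre-support values | 1.5(1−r) | (1−r)(1.5+r) |
| Adjusted for both pre-support values | (1−r)(1+2r)/(1+r) | 1−r² |

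Estimating two slopes multiplies the adjusted standard error by √(60/58) = 1.017 with 64 students (class and support in the model), and by √(29/27) = 1.036 for C versus D.

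**Example, r = 0.5, compound symmetry.** Adjusted variance is 0.5 × 2/1.5 = 0.667. Change has variance 1, so the ratio is √0.667 × 1.017 = 0.83, a 17% smaller standard error. The mean-of-both contrast has variance 0.75, so the ratio is √(0.667/0.75) × 1.017 = 0.96, a 4% reduction.

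**Reduction in standard error from adjustment, at r = 0.3/0.5/0.7/0.8.**

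| Comparator | Compound symmetry | AR(1) |
|---|---|---|
| Change from end of fall, N = 64 | 20/17/15/14% | 18/12/6/4% |
| Change from end of fall, C v D | 19/15/13/12% | 16/10/5/2% |
| Mean of both pre-support values, N = 64 | 8/4/1/0% | 14/12/11/10% |
| Mean of both pre-support values, C v D | 6/2/−0.5/−2% | 12/10/9/8% |
| Post-only, N = 64 | 6/17/34/45% | 3/12/27/39% |

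Against post-only the gain is nil where the variance removed only pays for the slopes, that is, where the adjusted variance times 60/58 equals 1. This happens at r of about 0.14 (compound symmetry) or 0.18 (AR(1)). At r = 0 adjustment costs 1.7%.

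**C versus D in outcome units, r = 0.5.** The 95% half-width for change is 2.04 × √(2/16) = 0.72 SD. Adjusted it is 0.61 SD (compound symmetry) or 0.65 SD (AR(1)). The mean-of-both contrast gives 2.04 × √(0.75 × 2/16) = 0.63 SD under compound symmetry and 0.72 SD under AR(1).

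**Knowledge of assignment.** Of class students the plan says: "Participants will then be informed of their group assignment (active with follow up or active no follow up". This apparently precedes Phase 1. Suppose it shifts the end-of-Phase-1 value by 0.20 SD in A relative to B and the shift does not last. The bias in A versus B is then −0.20 for change from end of fall and −0.10 for the mean-of-both contrast. With both covariates it is −0.20 × r/(1+r), or −0.05 to −0.09, under compound symmetry, and −0.20 × r, or −0.06 to −0.16, under AR(1). It is 0 for a post-only or baseline-only analysis.

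**Clustering in A versus B.** Thirty-two class students in four periods make 8 per period. The design effect is 1 + 7 × ICC = 1.35 or 1.70 at an assumed ICC of 0.05 or 0.10, with 2 degrees of freedom between periods (t = 4.30). Number of Subjects can instead be read as one class per arm: "One group of each intervention arm (four) would give us data on approximately 64 subjects". Support would then be confounded with class, and no degrees of freedom would be left.

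**The case against.** The strongest reply concerns the comparator. A reader might infer that the planned ANOVA must give wider intervals than the collected data allow. The documents do not support that, because they do not say which contrast will be tested. If follow-up is set against the mean of both pre-support values and correlations are equal, almost nothing is left to gain at high correlation, and C versus D could lose up to 2%. This objection stands and limits the claim.

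Also sound: a between-subjects comparison of follow-up values alone carries no bias from early knowledge of assignment, whereas adjusting for the end-of-Phase-1 value may introduce some. A linear model does not suit a weekly cooking count, for which the plan already names a suitable model. The 64-student gains ignore clustering, which adjustment does not cure: in a simulation with an ICC of 0.05, ignoring it gave type I error of 7-11%.

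Finally, this is a pilot without a power claim, and ANOVA output can still supply variances for the next study. That lowers the priority. It does not remove the case for a low-cost improvement.

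**Conclusion.** The point holds as a precision improvement for support versus no support, under Aim 2 and the support part of Aim 3. The gain in standard error runs from about zero, or a slight loss in C versus D, to about 20% against a change or mean-of-both contrast. Against a post-only comparison it is larger at moderate to high correlation and vanishes at very low correlation. All of this rests on assumed correlations, complete data and no clustering, and it is approximate for counts.

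Three further inferences should be resisted. No stated figure is wrong, and the planned ANOVA is not shown to be invalid. The gain does not extend to meal kits versus recipes, which is a within-person comparison in fixed order: "After six weeks of receiving meal kits, groups will receive five healthy recipes via email per week". Nor does it carry over to class versus control, because the end-of-Phase-1 value is itself affected by the classes.

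**What to change.** 1. For food agency, diet quality, intuitive eating and perceived stress, analyse support versus none in Phases 2-3 with a linear mixed model: support-by-phase terms, class condition, class period as a random effect in class students, and baseline and end-of-Phase-1 values as covariates. State the missing-at-random assumption.
2. For weekly cooking frequency, keep the generalized linear mixed model already named, apply it to Aim 2, and add pre-support frequency as a covariate.
3. Name C versus D, which is individually randomised, as the support estimate with a clearly valid standard error. Report the pooled and A versus B estimates with the caveat that support follows class period there and periods are few.
4. Report a baseline-only adjusted sensitivity analysis, and say that it can be less precise than the change score: under AR(1) its standard error ratio to change is √((1−r⁴)/(2(1−r))), or 1.13 at r = 0.7 before slope cost.
5. Do not apply the end-of-Phase-1 adjustment to class versus control.
6. Reconcile the survey-timing sentence in Procedures with the opening summary, Study Design, Quantitative Measures and the survey-administration text, since the end-of-Phase-1 covariate depends on it. Say which groups form the control group in the Aim 2 sentence.

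The cost is analysis-plan wording and slightly more modelling work, with no new data items. The downsides are reliance on missing at random, the caveat about the Phase 1 value, and a gain that may be near zero at high correlation.

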Hypothesis 3: Participants receiving cooking support will have lower scores on a measure of perceived stress than participants who do not receive cooking support. This will be true at all measurement time points.

Aim 4: To explore the reasons why students cook or do not cook.

Hypothesis 4: There will be common themes defining why student choose to cook or not cook at home.

Study Design: Describe the research design, including a description of any new methodology and its advantage over existing methodologies.

We propose a randomized trial to evaluate whether cooking classes produce greater gains in cooking skills and food agency compared to a control condition, as well as whether provision of meal delivery and recipes result in more frequent cooking than no meal delivery or recipe provision. We will randomize 64 students to either the intervention condition where they will take part in six weeks of hands on cooking classes, or the control condition where they will receive no cooking instruction during the fall semester. Following the completion of cooking classes and the start of the spring semester, one active cooking (treatment) group and one control group will receive another 12 weeks of intervention while the other two groups will receive no further instruction. The two continued intervention groups will be subscribed to a meal delivery service for six weeks, and then receive only recipes for another six weeks. Assessments will be conducted at baseline and following each phase of the intervention for all groups.

Study Population

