Cooking and Food Provisioning Action Scale (CAFPAS): The CAFPAS scale measures cooking and food preparation practices or the degree to which individuals can set and achieve cooking and food provisioning goals. The CAFPAS includes 28 items with three subscales: Food Self-Efficacy, Food Attitude, and Structure. The CAFPAS scale has been shown to predict reported meals cooked per week and has adequate internal validity and test-retest reliability.⁴³

Perceived Stress Scale (PSS) – The PSS is a reliable and valid measure of perceived stress in adults including college students.⁵⁹ It is composed of ten questions that assess how often one perceives various forms of stress such as feeling unable to control important events, being upset by something unexpected, and feeling nervous.⁵⁹ Every six weeks participants, during the study period, participants will fill out the PSS, so any impact of cooking practice on stress can be illuminated.

The Cooking Perceptions and Behaviors Questionnaire: The Cooking Perceptions and Behaviors questionnaire is a 53-item survey designed to assess three factors: Perceptions of Cooking, Cooking Confidence and Attitudes, and Cooking Behaviors. This survey has been used in previous research to measure cooking perceptions and behavior.⁴⁴

Intuitive Eating Scale-2: The Intuitive Eating Scale-2 is a 23-item survey designed to assess the degree to which someone is able to listen to hunger and fullness cues when they decide what, when, and how much to eat.⁴⁵ The scale is composed of four sub-scales, Unconditional Permission to Eat, Eating for Physical Rather Than Emotional Reasons, Reliance on Hunger and Satiety Cues, and Body-Food Choice Congruence. This survey has been used in previous research with college students.⁴⁵

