After the final cooking class, participants in groups B and D will receive no further instruction, though they will be asked to complete surveys and data collection through the remainder of the study phases. Phase 2 will begin in mid-January 2020. Participants in Groups A and C will receive weekly meal kit deliveries for 6 weeks. Meal kits will be delivered to students’ homes once per week and will include the ingredients and instructions for preparing 3 separate meals. Phase 3 will be immediately following phase 2. Participants in groups A and C will receive an email at the beginning of each week for the next six weeks that provides them with 5 healthy recipes developed by the study team. Students will generally receive the same recipes though; modifications may be made for participants with special dietary restrictions.

Facilities and Equipment Needed

Cooking Labs – The cooking classes and demonstrations will take place in the Nutrition and Food Sciences teaching kitchen located in the Marsh Life Science building. The teaching kitchen has room for 16 students to complete hands on cooking labs, and an additional space where students can get directions, eat, and watch cooking demos. The kitchens are fully stocked with the necessary kitchen equipment.

Follow-up Data Collection

Participants will be alerted by email to complete their follow-up assessment questionnaires which are anticipated to take approximately 30 minutes to complete and 3 days of the ASA24 (approximately 30 minutes per day).

All participants will be offered small incentives such as cooking equipment, cookbooks, gift cards, etc. (valued at approximately \$ 5-25) after completion of the follow-up data collection. Those in the Control Group will also receive a small incentive for completing their baseline measures.

For research involving survey, questionnaires, etc.: Describe the setting and the mode of administering the instrument and the provisions for maintaining privacy and confidentiality. Include the duration, intervals of administration, and overall length of participation. (describe and attach all instruments)

Not applicable

Questionnaires and ASA-24 logs will be administered at baseline and at the end of each study phase.

Photo elicitations and cooking frequency surveys will be administered weekly during the active study phases.

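### Aim 3: the repeated measures ANOVA names no contrast for Hypothesis 3, although the supported groups change from A and B in Phase 1 to A and C in Phases 2 and 3

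*Combined protocol and SAP*

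**What the plan says.** Hypothesis 3 appears under Objectives and again under Statistical Considerations. It predicts lower perceived stress in participants who receive cooking support than in those who do not, and ends: "This will be true at all measurement time points". The analysis for Aim 3 is a single sentence: "A repeated measures ANOVA will be used to determine differences both between groups and over time in scores of perceived stress". It does not say whether group has two or four levels, and it names no contrast.

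Who is supported when has to be read from the design sections:

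- Phase 1 (Control Condition paragraph): "Those in the Control Condition will receive no cooking support over the fall semester". The supported groups are therefore A and B.
- Phases 2 and 3 (Follow up Support): "The active and control groups receiving follow up support (groups A and C) will receive six weeks of meal kits", followed by weekly recipes.
- For the other two groups (Intervention section): "participants in groups B and D will receive no further instruction".

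On timing, the description of the Perceived Stress Scale (PSS) says: "Every six weeks participants, during the study period, participants will fill out the PSS". The survey-administration section agrees: "Questionnaires and ASA-24 logs will be administered at baseline and at the end of each study phase". Procedures differs: "Surveys will be administered through the study REDCap website at baseline and study end". The PSS is also listed among the baseline measures under Inclusion/Exclusion Criteria.

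**The concern.** The hypothesis is a directional statement about supported minus unsupported participants at each assessment. Membership of those two sets is not fixed. After Phase 1, group B moves from supported to unsupported and group C moves the other way.

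The tests usually read off a repeated measures ANOVA do not follow that movement. A between-group main effect averages each group over periods with and without support. A group-by-time interaction shows that profiles differ somewhere, but not at which assessment or in which direction. Neither is the quantity in the hypothesis. Unless the contrasts are written down, the comparison reported for Aim 3 can be chosen after the data are seen, and the estimate carried into the larger study may not be the one intended. Read literally, the hypothesis also covers the baseline PSS, when nobody has been supported.

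**Working it through.** **Inputs from the documents.** Four groups of 16 give 4 × 16 = 64, which reproduces the stated sample size. There are four PSS assessments if the scale is given at baseline and at each phase end. No effect size, SD, correlation, alpha or dropout is stated; those used below are assumptions.

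**Support status at each assessment (1 = currently supported).**

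| Group | Baseline | Phase 1 | Phase 2 | Phase 3 |
|---|---|---|---|---|
| A | 0 | 1 | 1 | 1 |
| B | 0 | 1 | 0 | 0 |
| C | 0 | 0 | 1 | 1 |
| D | 0 | 0 | 0 | 0 |

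B and C change status: 16 + 16 = 32 of 64. Each post-baseline assessment still splits 32 v 32 by current support.

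**Main effects with no carry-over.** Let d be the reduction in PSS while supported, equal across types of support. The four-assessment averages are A 3/4 d, B 1/4 d, C 2/4 d, D 0.

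- Class v control: (0.75 + 0.25)/2 − (0.50 + 0)/2 = 0.25d.
- Follow-up v none: (0.75 + 0.50)/2 − (0.25 + 0)/2 = 0.50d.
- By assessment, (A+B) minus (C+D), as group averages, is 0, d, 0, 0. It is zero in Phases 2 and 3 even when the hypothesis is true after baseline.

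**Main effects with additive carry-over k from the classes.** In Phases 2 and 3, A = d + k, B = k, C = d, D = 0. Take k = d.

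- Four-assessment averages: A 5/4 d, B 3/4 d, C 2/4 d, D 0. Class main effect: (1.25 + 0.75)/2 − (0.50 + 0)/2 = 0.75d.
- Post-baseline averages: A 5/3 d, B d, C 2/3 d, D 0. Class main effect: (5/3 + 1)/2 − (2/3 + 0)/2 = 1, that is, d.

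So the class main effect over four assessments runs from 0.25d to 0.75d as k goes from 0 to d, and without baseline it can reach d.

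**Omnibus interaction.** Consider a group difference at baseline only (1, 0, 0, 0), at Phase 1 only (0, 1, 0, 0), or reversed at Phase 1 (0, −1, 0, 0). Each has centred sum of squares 0.75² + 3 × 0.25² = 0.75, so the test cannot tell them apart.

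**Phase-specific contrasts.**

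- (A+B)/2 − (C+D)/2 at the end of Phase 1 is d.
- (A+C)/2 − (B+D)/2 at the end of Phases 2 and 3 is [(d + k) + d]/2 − [k + 0]/2 = d. Additive carry-over cancels because each side has 16 class and 16 control participants.
- If effects do not add, for example A = B = C = d and D = 0, the same contrast is d − d/2 = d/2, while A − B = 0 and C − D = d. The pooled figure then hides two different answers.

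**Precision.** Assume all 64 are analysed, SD 1, correlation r with baseline and no clustering by class. The variance of each pooled contrast is (1/4) × 4 × (1/16) × (1 − r²) = (1 − r²)/16. With t(59) = 2.001:

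| r | SE | 95% half-width |
|---|---|---|
| 0.3 | 0.2385 | 0.477 SD |
| 0.5 | 0.2165 | 0.433 SD |
| 0.7 | 0.1785 | 0.357 SD |

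A v B or C v D alone is 16 v 16, so these widths are multiplied by √2, giving about 0.50 to 0.67 SD. Without baseline adjustment, 32 v 32 at two-sided 0.05 has power of about 22%, 52% and 89% for d = 0.3, 0.5 and 0.8 SD at one assessment.

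**The case against.** The strongest reply is that the sentence is brief rather than wrong. It promises differences between groups and over time. It does not say that a main effect or an omnibus interaction will decide the hypothesis. A four-group-by-time model holds every cell mean the contrasts need, and follow-up contrasts are ordinary practice. This stands: a reader might infer that the planned ANOVA cannot test Hypothesis 3, and the documents do not support that. What remains is that no follow-up contrast is named for stress, and the right one changes between phases.

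A reader might also infer that a group main effect must understate the effect of support. That holds under no carry-over, which the documents do not assume. Aim 2 and Hypothesis 2b expect class gains to be maintained for food agency, cooking frequency and diet quality. If stress behaved likewise, the class main effect could reach d. Nor do the phase-specific contrasts always recover d, since that needs class and follow-up effects to add.

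The hypothesis does not say whether receiving support means currently or ever. Under ever supported, the comparison from Phase 2 is A+B+C v D (48 v 16) and only C's 16 participants switch. The Control Condition wording, which ties absence of support to the fall semester, fits current support better. Under either reading the comparison changes after Phase 1 and is not named. One overview sentence gives classes or demonstrations to all conditions, but it conflicts with the control described in the same section and in Study Design, and does not settle the matter.

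Finally, this is the third aim of a pilot with no power calculation. That limits the weight of the point, but the pilot's data are meant to size a larger study, so its estimates should match its hypotheses.

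**Conclusion.** The point holds as a gap in specification. Hypothesis 3 needs three phase-specific comparisons whose membership changes, and the Aim 3 analysis names none. On the current-support reading, 32 of 64 participants switch status. The structural mismatch does not depend on any effect size: a fixed-group main effect mixes supported and unsupported periods, and an omnibus interaction has no direction or location.

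The size of any distortion does depend on assumptions. With an equal effect and no carry-over, the main effects over four assessments are 0.25d (class) and 0.50d (follow-up); with full additive carry-over, the post-baseline class effect is d. No single dilution figure should be quoted as the consequence.

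Naming the contrasts corrects the target but adds no information. Half-widths of about 0.36 to 0.48 SD remain, and would be wider with dropout or clustering by class. The change should be made, because it is cheap and removes a choice that could otherwise follow the data.

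**What to change.** 1. Define receiving support as current support, and restrict Hypothesis 3 to post-baseline assessments.
2. Pre-specify (A+B) minus (C+D) at the end of Phase 1, and (A+C) minus (B+D) at the end of Phase 2 and at the end of Phase 3, each with a 95% confidence interval. Take them from a four-group-by-phase repeated-measures model of post-baseline PSS with baseline PSS as covariate.
3. State the decision rule: the claim about all time points is supported only if all three contrasts favour support, each interval lying wholly on the side of lower stress. An all-must-hold rule needs no multiplicity adjustment, but its power cannot exceed that of the weakest contrast. Otherwise report the three as pilot estimates.
4. Report A v B and C v D separately as well, because the pooled contrast equals d only if class and follow-up effects add.
5. Label class v control as non-randomised. Under Consent Procedures, controls are recruited from applicants who did not go on with recruitment for the classes. Baseline adjustment does not remove that selection; give a change-from-baseline analysis of this contrast as a sensitivity check.
6. State that C v D is randomised within the Control Condition, while A v B is assigned by class period (Procedures).
7. Reconcile the survey timing in Procedures with the PSS description and the survey-administration section. The Phase 1 and Phase 2 contrasts can be estimated only if the PSS is collected at each phase end.

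The cost is wording in the analysis section and one reconciled schedule statement. No participants are added, and no data beyond PSS at each phase end are needed.
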